## 3.6. Missing Data and Outliers

# 3.6.1. Missing Data

A missing datum for a given study analysis window may be due to any of the following reasons:

- A visit occurring in the window but data were not collected or were unusable
- A visit not occurring in the window
- A subject prematurely discontinuing from the study before reaching the window

In general, missing data will not be imputed unless methods for handling missing data are specified. Exceptions are presented in this document.

For the secondary endpoints of the percent changes from baseline in hip BMD and spine BMD in a subset of subjects, urine beta-2-microglobulin to creatinine ratio, and urine RBP to creatinine ratio, the distribution of UP and UPCR categories and the change from baseline in serum creatinine, missing values will be imputed using the last observation carried forward (LOCF) method and baseline observation carried forward (BlOCF) method.

# The algorithm for LOCF is as follows:

- If a postbaseline value is missing in an analysis visit window, the missing value will be replaced with the last on-treatment value (ie, data collected up to 30 days after permanent discontinuation of study drug or all available data for subjects who were still on study drug) observed before the analysis visit window that has the missing value.
- Baseline values will be carried forward to impute the postbaseline value at a specific visit, if there is no nonmissing postbaseline observation collected prior to that visit.

The algorithm for BlOCF is as follows:

• Baseline values will be carried forward to impute the missing postbaseline value at a specific visit.

For missing or incomplete last dosing date of study drug, imputation rules are described in Section 3.8.1. For missing or incomplete start or end dates of study drug for the computation of study drug interruptions, imputation rules are described in Section 4.2.2.2. The handling of missing or incomplete dates for AE onset is described in Section 7.1.5.2, and for prior and concomitant medications in Section 7.6. Imputation rules for missing DBS concentration at the time of HIV diagnosis are as described in Appendix 9.

#### **3.6.2. Outliers**

Outliers will be identified during the data management and data analysis process. No prespecified sensitivity analyses to evaluate the impact of outliers are planned. All data will be included in the data analysis.

# 3.7. Data Handling Conventions and Transformations

In general, age (in years) on the date of the first dose of study drug will be used for analyses and presentation in listings. If a randomized subject was not dosed with any study drug, the randomization date will be used instead of the first dosing date of study drug. For screen failures, the date the informed consent was signed will be used for age calculation. If only the birth year is collected on the CRF, "01 July" will be used for the unknown birth day and month for the purpose of age calculation. If only birth year and month are collected, "01" will be used for the unknown birth day.

Laboratory data (non-PK) that are continuous in nature but are less than the lower limit of quantitation (LOQ) or above the upper LOQ will be imputed as follows except for urine creatinine:

- A value that is 1 unit less than the LOQ will be used to calculate descriptive statistics if the datum is reported in the form of "< x" (where x is considered the LOQ). For example, if the values are reported as < 50 or < 5.0, values of 49 or 4.9, respectively, will be used to calculate summary statistics. An exception to this rule is any value reported as < 1 or < 0.1, etc. For values reported as < 1 or < 0.1, a value of 0.9 or 0.09, respectively, will be used to calculate summary statistics.
- A value that is 1 unit above the LOQ will be used to calculate descriptive statistics if the datum is reported in the form of "> x" (where x is considered the LOQ). Values with decimal points will follow the same logic as above.
- The LOQ will be used to calculate descriptive statistics if the datum is reported in the form of " $\leq$  x" or " $\geq$  x" (where x is considered the LOQ).

For urine creatinine, a value of "< 1" is handled as a missing value in its summary and the calculation of related ratios.

HIV-1 RNA results of 'No HIV-1 RNA detected' and "<20 cp/mL HIV-1 RNA Detected" will be imputed as 19 copies/mL for analysis purposes. HBV DNA results of "<20 IU/mL HBV DNA detected" or "No HBV DNA detected" will be imputed as 19 IU/mL for analysis purposes. HCV RNA results of "<15 IU/mL HCV RNA detected" or "No HCV RNA detected" will be imputed as 14 IU/mL for analysis purposes.

Natural logarithmic transformations will be used for analyzing PK and PBMC trough concentrations. Concentration values that are below the lower limit of quantitation (BLQ) will be presented as "BLQ" in the concentration listing. Trough PK, trough PBMC and DBS RBC concentration values that are BLQ will be treated as one-half of the lower LOQ.

The following conventions will be used for the presentation of summary and order statistics for PK and PBMC concentrations:

- If at least 1 subject has a concentration data value of BLQ for the time point, the minimum value will be displayed as "BLQ".
- If more than 25% of the subjects have a concentration data value of BLQ for a given time point, the minimum and Q1 values will be displayed as "BLQ".
- If more than 50% of the subjects have a concentration data value of BLQ for a given time point, the minimum, Q1, and median values will be displayed as "BLQ".

- If more than 75% of the subjects have a concentration data value of BLQ for a given time point, the minimum, Q1, median, and Q3 values will be displayed as "BLQ".
- If all subjects have concentration data values of BLQ for a given time point, all order statistics (minimum, Q1, median, Q3, and maximum) and summary statistics will be displayed as "BLQ".

# 3.8. Analysis Windows

# 3.8.1. Definition of Study Day

**Study Day 1 (DB phase)** is defined as the day when the first dose of randomized study drug (ie, *F/TAF or Placebo-to-match F/TAF*, *F/TDF or Placebo-to-match F/TDF*) was taken, as recorded on the Study Drug Administration eCRF form.

**Study Day 1 (OLE phase).** For subjects who were treated in the OLE phase, Study Day 1 is defined as the day when the first dose of OLE phase study drug (ie, F/TAF) was taken, as recorded on the "Extension Phase" Study Drug Administration eCRF.

**Study Days** are calculated relative to Study Day 1 for each phase. For events that occurred on or after the Study Day 1 date, the number of study days is calculated as (visit date minus Study Day 1 date plus 1). For events that occurred prior to DB phase Study Day 1, the number of study days is calculated as (visit date minus Study Day 1 date).

**Last Dose Date (DB phase)** is the latest of the blinded study drug end dates (administering ≥1 tablet per day) recorded on the Study Drug Administration eCRF form with "Permanently Withdrawn" box checked for subjects who prematurely discontinued or completed study drug in the blinded treatment study phase according to the Study Drug Completion eCRF.

If last dose date is completely missing (ie, due to lost to follow-up) for subjects who prematurely discontinued or completed blinded study drug at the data cut date in the DB phase, the latest of study drug start dates and end dates, the clinic visit dates, and the laboratory visit dates excluding the date of 30-day follow-up visit, from the DB phase data, will be used to impute the DB phase last dose date. For other partial missing last dose date, please see the programming specifications for imputation rule details.

If the DB phase last dose date is after the first dose date of the OLE phase, use the day before the first dose date of the OLE phase to impute it.

Last Dose Date (OLE phase) is defined as the latest of the OLE phase study drug end dates recorded on the "Extension Phase" Study Drug Administration eCRF with "Permanently Withdrawn" box checked for subjects who prematurely discontinued study drug according to the "Extension Phase" Study Drug Completion eCRF. This date will only be available for subjects treated in the OLE phase of the study. If the last dose date is missing for subjects who prematurely discontinued study drug in the OLE phase of the study, the latest of nonmissing OLE phase study drug start dates and end dates, the clinical visit dates, and the laboratory visit dates, excluding the date of 30-day follow-up visit, from the OLE phase data, will be used to impute the OLE phase last dose date.

**Last Study Date** is the latest of the randomized or OLE phase (if available) study drug start dates and end dates, the clinic visit dates, and the laboratory visit dates, including the 30-day follow-up visit date, for subjects who prematurely discontinued study or who completed study according to the Study Completion eCRF.

Last At-Risk of HIV Infection Date (DB phase) is (1) the date of HIV infection diagnosis as defined in Section 6.2.2 for subjects who have been diagnosed as infected with HIV during the DB phase or (2) the date of the last post-baseline HIV laboratory test (either local rapid or Covance HIV laboratory tests, including the 30-day follow-up visit date) during the DB phase for subjects who have not been infected with HIV during the DB phase.

Last At-Risk of HIV Infection Date (OLE phase) is (1) the date of HIV infection diagnosis as defined in Section 6.2.2 for subjects who have been diagnosed as infected with HIV during the OLE phase or (2) the date of the last post-baseline HIV laboratory test (either local rapid or Covance HIV laboratory tests, including the 30-day follow-up visit date) during the OLE phase for subjects who have not been infected with HIV.

**Baseline value** is defined as the last value obtained on or prior to Study Day 1 for each phase for all assessments, except for DXA BMD. The baseline value for DXA BMD is defined as the last value obtained on or prior to Study Day 14 of each phase.

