3.2. Study Design

This protocol describes a randomized, double-blind comparison of the safety and efficacy of F/TAF versus F/TDF administered once daily for at least 96 weeks in HIV-1–negative adult MSM or TGW (male at birth) who have sex with men and are at risk of HIV-1 infection.

All participants must meet all eligibility criteria in order to receive treatment in the study. Once randomized to receive treatment in the study, all participants must return to the study center for required visits at Weeks 4, 12, and every 12 weeks thereafter.

All participants will remain blinded to study drug for at least 96 weeks. The primary endpoint data will be collected and analyzed when all participants have a minimum follow up of 48 weeks and 50% of the participants have 96 weeks of follow up after randomization.

Once all participants have at least 96 weeks of follow up after randomization and upon notification by Gilead, all participants will return to the study center for an end of blinded treatment phase visit (may coincide with their next scheduled visit).

Participants who are still on blinded study drug at the end of blinded treatment phase visit will be offered entry into the OL phase of the study. CCI

Participants who have discontinued study drug prior to the end of blinded treatment phase visit due to HIV infection will be eligible to continue participation in the OL phase up to OL Week 48, but will not be administered F/TAF once daily. From OL Week 48 participants who acquire HIV must complete the early study drug discontinuation (ESDD) visit and discontinue the study at the 30-Day Follow-up visit, 30 days after the last dose of study drug. Participants who have discontinued study drug for any other reason prior to the end of blinded treatment phase visit will not be eligible to participate in the OL phase.

[figure not shown]
CCI

During the blinded treatment phase, participants may choose to continue to participate in the study without taking study drug (“on-study, off-study drug”). Participants who permanently discontinue study drug and continue to attend normal study visits (at minimum one visit at least 30 days after last dose) are not required to complete the follow-up visit. Any participant who has an ESDD visit and who will not continue participating in the study, or any participant who will not continue participation in the OL phase of the study, must complete the 30-Day Follow-Up visit 30 days after the last dose of study drug.

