## 4.2.3.1. Adherence to Study Drug Regimen During Study via Pill Counts

For the DB phase, study drug regimen (in-study) prescribed adherence will be computed based on pill counts for active drug only (ie, study drug regimen in Treatment Group 1 includes 1 study drug: *F/TAF active*. Study drug regimen in Treatment Group 2 includes 1 study drug: *F/TDF active*. The numbers of pills of study drug dispensed and returned are captured on the Study Drug Accountability eCRF.

The level of prescribed adherence (or in-study adherence) to the study drug regimen will be determined by the total amount of study drug administered relative to the expected total amount of study drug (1 pill per day for the duration of study participation based on the protocol) and will be calculated from first study drug start date to the end date defined as the latest of the study drug start dates and end dates, the clinic visit dates, and the laboratory visit dates during the DB phase, excluding the 30-day follow-up visit date. If the subject has been diagnosed with HIV infection during the DB phase, the later date of either the 1) HIV diagnosis date or 2) the DB phase last dose date will be used as the end date. Per study design, subjects that have been diagnosed with HIV infection must immediately discontinue study drug but may remain in the study.

The level of prescribed adherence will be expressed as a percentage using the following formula:

$$Prescribed\ Adherence\ (\%) = \frac{Total\ Amount\ of\ Study\ Drug\ Administered}{Total\ Amount\ of\ Study\ Drug\ Expected\ While\ Participating\ in\ Study} \times 100$$

- [1] Total amount of study drug administered is the number of pills dispensed minus the number of pills returned.
- [2] Total amount of study drug expected while participating in the study is calculated as the daily number of pills prescribed for the study drug multiplied by the duration of study participation defined as from first dose date to the end date defined as the latest of the study drug start dates and end dates, the clinic visit dates, and the laboratory visit dates excluding the 30 day follow up visit date. If the subject has been diagnosed with HIV infection, the later date of either the 1) HIV diagnosis date or 2) last dose date will be used as the end date.

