### 6.2.6. Sensitivity Analyses of the Secondary Efficacy Endpoint While On-Treatment (HIV Infection Rate Ratio Method)

A sensitivity analysis of the secondary endpoint will be based on HIV infections occurring while subjects are on-treatment during the double-blinded phase of the study using the PP analysis set. This on-treatment analysis will include HIV infection events and follow-up times occurring between first dose date to DB phase last dose date plus 10 days (for F/TDF) or plus 16 days (for F/TAF) and exclude:

- 1) HIV-1 infection events and follow-up time during the OLE phase.
- 2) Off study drug PrEP (off-treatment) HIV infection events and follow-up time defined as events and follow-up time occurring greater than 10 days for (F/TDF) or 16 days (for F/TAF) after permanent discontinuation of study drug (Appendix 7).
- 3) HIV infections and follow-up time occurring after subjects initiated any non-study PrEP treatment that includes the period after permanent discontinuation of study drug (including commercial drugs like Truvada®, generic Truvada, or investigational drugs like cabotegravir for PrEP with a stop date that is either ongoing or after permanent discontinuation of study drug).

The HIV infection incidence rate per 100 person-years of follow-up will be computed as the number of subjects with on-treatment HIV infection divided by the sum of all subjects' years (where a year is 365.25 days) of on-treatment follow-up while at risk of HIV infection in study. The duration of on-treatment follow-up while at risk of HIV infection is defined as the time between Day 1 (first dose date) and the end date (end date Day 1 date +1) where end date is defined as:

- For subjects who have been diagnosed as infected with HIV while on-treatment: the date of the on-treatment HIV infection which will be the date of the HIV infection diagnosis (as defined in Section 6.2.2).
- 2) For subjects who have not been infected with HIV while on-treatment, the earlier of:
  - a) last dose date + 10 days for F/TDF or + 16 days for F/TAF for subjects who permanently discontinued study drug (including subjects with off-treatment HIV infection)
  - date of last post-baseline HIV laboratory test (either local or Covance HIV laboratory tests, which may include the 30-day follow-up visit date) for subjects who have not permanently discontinued study drug

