- 12) Please note, "Not Permitted", "Unknown", "Not Applicable", "Not Done" or missing categories will be excluded for percentage calculation and also excluded for p-value generation for categorical data analysis (ie, CMH test or Fisher exact test). For the number of subjects with each syphilis stage and syphilis status summarized among subjects with a syphilis diagnosis, no p-values will be generated.
- 13) SAS code for the treatment comparison for duration of exposure. The p-value from log rank test should be used.

```
proc lifetest data=ADSL method=km;
   time TRTDURD*ESDD(0); /*Derive ESDD from COMT01FL, where ESDD = 0
   indicates censored observation (ie, subject is still on study drug)*/
   Strata TRT01AN;
   label TRTDURD = "Duration of Exposure (Days)";
run;
```

- 14) Last Dose Date and Last Study Date
  - a) Last Dose Date (ie, TRTEDTC, TRTEDT, TR01EDT or TR01EDTC) in ADSL was defined in Section 3.8.1 for subjects who prematurely discontinued or completed study drug in the 'blinded treatment' study phase.

If study drug start date or end date are partially missing (ie, only year and month are known), the day will be imputed as 15 for the purpose of this analysis.

For subjects with a partial last dosing date (ie, month and year of last dose are known), use the max (the dispensing dates of study drug bottles, study drug start dates and end dates, imputed end date of last dose [day imputed as 15]) as the final imputed last dose date. (However, if dispensing date's month is after last dose date's month, data query is needed.)

For subjects where only the year of the last dosing date is known), then impute the last dose date based on the below:

Condition	Last dose date (year only) is imputed as
The year of the last dose is equal to the year of the last visit*	Maximum of study drug start dates and end dates, clinic visit dates and laboratory visit dates excluding the 30-day follow-up visit
The year of the last dose is before the year of the last visit*	December 31st of the last dose year
The year of the last dose is after the year of the last visit*	Data query is needed. If this remains unchanged after query, impute as:  January 1 st of the last dose year

\*Last visit is defined as the maximum of clinic visit dates and laboratory visit dates excluding the 30 day follow up visit.

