If the date of last dose is completely missing, use the maximum of study drug start dates and end dates, clinic visit dates, and laboratory visit dates excluding the 30-day follow-up visit to impute the last dose date.

If subject died and the death date is complete (ie, not partial date) and before the imputed last dose date, the complete death date should be used as the imputed last dose date.

If subject has been diagnosed with HIV infection and before the imputed last dose date (year only or month/year only known), the date of HIV diagnosis should be used as the imputed last dose date. Per study design, subjects that have been diagnosed with HIV infection must immediately discontinue study drug.

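### A last dose date that is completely missing, or known only to the last-visit year, is imputed as the last visit even for participants who stopped drug but stayed in the study

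*SAP*

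**What the plan says.** SAP Section 3.8.1 opens the rule with its reason: "If last dose date is completely missing (ie, due to lost to follow-up) for subjects who prematurely discontinued or completed blinded study drug". The value used is the latest of the study drug dates and "the clinic visit dates, and the laboratory visit dates excluding the date of 30-day follow-up visit, from the DB phase data, will be used". Appendix 12 item 14 repeats this: "If the date of last dose is completely missing, use the maximum of study drug start dates and end dates, clinic visit dates".

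Item 14 treats partial dates differently according to what is known:

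- **Month and year known:** the latest of the dispensing dates, the study drug dates and day 15 of the month. Visit dates play no part.
- **Year only, same year as the last visit:** "Maximum of study drug start dates and end dates, clinic visit dates and laboratory visit dates excluding the 30-day follow-up visit".
- **Year only, earlier than the last-visit year:** 31 December of the last-dose year.
- **Year only, later than the last-visit year:** query, then 1 January of the last-dose year.

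If HIV was diagnosed before an imputed date that was year-only or month/year-only, "the date of HIV diagnosis should be used as the imputed last dose date". This cap is not written for completely missing dates.

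Section 6.2.6 then ends on-treatment follow-up of uninfected participants at "last dose date + 10 days for F/TDF or + 16 days for F/TAF for subjects who permanently discontinued study drug", if nothing earlier applies, and uses the same window to decide which infections count.

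Protocol Section 3.2 lets participants remain in the blinded phase without taking drug. It also excuses one group from the 30-day follow-up visit: "Participants who permanently discontinue study drug and continue to attend normal study visits (at minimum one visit at least 30 days after last dose").

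**The concern.** The imputation suits someone who disappears, because the last contact is then a fair upper limit for the last dose. It does not suit someone who stops drug and keeps attending every 12 weeks. The one safeguard, leaving out the 30-day follow-up visit, does not protect that person, who need not have that visit. Every later off-drug visit is an eligible date. Item 14's branch for a stop year before the last-visit year shows that the SAP expects visits after stopping.

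The rules also run the wrong way. With month and year known, the date is tied to drug supply. With less information, supply is dropped and visits take its place, so poorer data give longer exposure.

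The diagnosis cap has a related gap. SAP Section 4.2.3.1 says that "subjects that have been diagnosed with HIV infection must immediately discontinue study drug but may remain in the study". A completely missing date can nevertheless run past diagnosis to the last visit. That lengthens exposure, the expected pill count and the safety windows.

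At stake are the 6.2.6 rate ratio, duration of exposure and time to discontinuation, the 30-day adverse event and laboratory windows, and the renal data labelled on-treatment.

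**Working it through.** No sample size or power figure in the plan rests on this rule, so there is none to reproduce. The check applies the rules to hypothetical dates and then illustrates size.

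**1. Classification.** Inputs are the item 14 rules, the diagnosis cap for partial dates, and the +10 (F/TDF) and +16 (F/TAF) day windows of 6.2.6. The last dispensing is assumed to fall before the middle of the stop month, and no non-study PrEP is taken. With the true stop date, every row is off-treatment. Each cell gives the imputed last dose and the resulting status.

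| Stop | Diagnosis | Last visit | Completely missing | Year only | Month and year |
|---|---|---|---|---|---|
| 1 Mar 2017 | 1 Nov 2017 | 1 Dec 2017 | 1 Dec 2017, on | 1 Nov 2017, on | 15 Mar 2017, off |
| 1 Mar 2017 | 1 Nov 2017 | 1 Dec 2018 | 1 Dec 2018, on | 1 Nov 2017, on | 15 Mar 2017, off |
| 1 Mar 2017 | 1 Jun 2018 | 1 Dec 2018 | 1 Dec 2018, on | 31 Dec 2017, off | 15 Mar 2017, off |
| 1 Nov 2017 | 12 Jan 2018 | 1 Dec 2018 | 1 Dec 2018, on | 31 Dec 2017, off on F/TDF, on on F/TAF | 15 Nov 2017, off |
| 1 Mar 2017 | 2 Apr 2017, only at the 30-day visit | 1 Mar 2017 | 1 Mar 2017, off | 1 Mar 2017, off | 15 Mar 2017, off |

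In rows 1 to 4 the completely missing rule turns every off-treatment infection into an on-treatment one. The year-only rule does so in rows 1 and 2, and in one arm of row 4. The month/year rule never does.

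**2. Length per participant.** Take someone who stops just after the Week 24 dispensing (Day 168) and attends to Week 96 (Day 672). Assume three 30-tablet bottles per interval and no leftover tablets. Supply ends by Day 168 + 90 = Day 258. The false exposure is at least 672 − 258 = 414 days, plus the 10-, 16- or 30-day tail.

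**3. Number affected.** The documents give no count. The safety analysis set is 5,387, so about 2,694 per arm. An assumed 0.1% to 1% is 3 to 27 participants per arm. If each carried 414 days, that is 3 × 414/365.25 = 3.4 to 27 × 414/365.25 = 30.6 off-drug person-years per arm. Expected infections in that time are:

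- at 1.44 per 100 PY (planned F/TDF rate): 0.05 to 0.44
- at 6.96 per 100 PY (equal-weighted placebo rate, protocol Table 8-1): 0.24 to 2.1

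**4. Effect on the 6.2.6 ratio.** With equal person-time, SE(log RR) = √(1/a + 1/b) and the upper limit is RR × exp(1.96 × SE). The 10 events per arm are borrowed from the case-control power calculation in SAP Appendix 9; no document plans a count for 6.2.6.

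| Events (F/TAF v F/TDF) | RR | SE | Upper 95% limit |
|---|---|---|---|
| 10 v 10 | 1.00 | 0.447 | 2.40 |
| 11 v 10 | 1.10 | 0.437 | 2.59 |
| 12 v 10 | 1.20 | 0.428 | 2.78 |

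If off-drug infections enter both arms equally, the ratio is diluted. With an assumed true on-treatment ratio of 1.62 and m extra infections per arm, the observed ratio is (1.62E + m)/(E + m), where E is the F/TDF count:

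- E = 10: m = 1 gives 17.2/11 = 1.56; m = 5 gives 21.2/15 = 1.41
- E = 72 (2500 × 2 years × 1.44/100): m = 1 gives 117.64/73 = 1.61; m = 10 gives 126.64/82 = 1.54

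Dilution moves the estimate toward 1, which favours non-inferiority.

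**The case against.** The best defence is that the affected group may be nearly empty. Section 3.8.1 links a completely missing date to loss to follow-up, and those participants have no long run of later visits. Anyone who stops is asked to attend an ESDD visit within 72 hours (protocol Section 6.7.1). Sites must hold drug start and end dates in source (9.1.5), and confirmed infections trigger collection of all event records (6.11). Infected participants are therefore among the least likely to lack a stop date. This stands as an argument about number. It does not change the rule, which covers everyone who discontinued or completed drug.

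Four stronger readings are tempting, and the documents do not support them:

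- **That every year-only date becomes the last visit, or that any infection becomes on-treatment.** An earlier stop year gives 31 December, and infections beyond the 10- or 16-day window stay off-treatment (row 3). Infections found only at the 30-day visit (row 5), or after qualifying non-study PrEP, can also stay off-treatment.
- **That the diagnosis cap itself makes infections on-treatment.** It applies only when diagnosis already precedes the imputed date, and it only moves that date earlier. Its absence for completely missing dates does not change 6.2.6 person-time for infections counted as on-treatment, because their follow-up ends at diagnosis anyway.
- **That bone density results are contaminated.** Protocol Section 6.10 stops DXA scans after permanent discontinuation, so BMD is largely protected.
- **That the main comparison is at risk.** The full analysis set uses the diagnosis date or the last HIV test (SAP 6.2.3 and 6.2.5), not the last dose.

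**Conclusion.** The concern holds within limits. For completely missing dates, and for year-only dates in the last-visit year, the SAP assigns a wrong last dose date to a class of participants that the protocol allows. For a year-only date in an earlier year, the HIV misclassification reaches only infections up to 31 December of that year plus 10 or 16 days. Both rules are at odds with item 14's own month/year rule.

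Per participant the error can exceed a year. Over the whole trial it is probably small. The count is unknown, and two misclassified infections in one arm would need the top of the assumed 0.1% to 1% range, untreated incidence, and every affected participant still attending off drug. Because 6.2.6 is meant to remove off-drug infections and may rest on few events, the rule deserves correction, but it does not threaten the trial's main efficacy conclusion.

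**What to change.** In SAP Section 3.8.1 and Appendix 12 item 14, for completely missing and year-only dates:

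1. Impute the earliest available of the ESDD visit date, the last dispensing date plus the number of tablets dispensed, and the latest double-blind visit, kept within the recorded year when it is known.
2. Apply the HIV-diagnosis cap to completely missing dates as well as partial ones.
3. Report the number of imputed last dose dates by arm and by type of missingness.
4. List every infection whose on-treatment status rests on an imputed date, and repeat 6.2.6 with those infections classed as off-treatment.

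The cost is a few sentences and a few lines of programming, using visit and dispensing records that are already collected. The downside is slightly shorter exposure for participants who went on taking leftover tablets. If item 3 shows no such dates, nothing else changes.
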